E: The urine test for beta-human chorionic gonadotropin will be performed at the study site. All females are to be tested to assess eligibility prior to randomization and dosing. A urine pregnancy test will be conducted to assess eligibility ONLY if the CSL830_3001 End of Study Visit and the first visit of CSL830_3002 Treatment Period 1 (ie, Day 1) occur on different days.

Schedule of Events for “CSL830-Interrupted” Subjects ^A and “CSL830-Naïve” Subjects ^B

	Screening ^C	Treatment Period 1 ^D							Treatment Period 2 ^D							Follow-up ^E	
Week	-4 to -1	1	5	9	13	17	21	25	29	33	37	41	45	49	53	See Footnote E.	
Day	-28 to -1	1	4	29	57	85	113	141	169	197	225	253	281	309	337		367
Window (days)		+ 1	± 2	± 2	± 2	± 2	± 2	± 2	± 2	± 2	± 2	± 2	± 2	± 2	± 2		
Study center visit	X	X	X ^F		X		X		X	X		X		X		X	
Telephone contact				X		X		X			X		X		X		
Informed Consent / Assent (as applicable) ^G	X																
Inclusion / exclusion criteria	X	X															
Individual acute action plan ^H	X	X															
Monitor / Document HAE Attacks ^I	X																
Enrollment and randomization		X															
Demographics and medical history	X																
Physical examination	X				X				X	X		X				X	
Indwelling catheter (yes/no)	X															X	
Vital signs, including body weight ^J	X				X		X		X	X		X		X		X	
Assess risk of DVT and PE	X				X		X		X	X		X		X		X	
CCI									X							X	
CCI		X			X				X	X		X				X	
Clinical Laboratory Assessments ^K	X	X			X				X	X		X				X	
Dispense CSL830 / other supplies			X		X		X		X	X		X		X			
Confirm access to on-demand HAE med	X	X	X		X		X		X	X		X		X		X	
Assess for CSL830 dose increase			← ^M							← ^N							
Train subject / observe CSL830 admin ^L		X	X														
CSL830 accountability		X	X		X		X		X	X		X		X		X	
Prior and concomitant therapy	←																
Adverse events	←																
Dispense eDiary		X															
Review eDiary / record attacks in eCRF			X		X		X		X	X		X		X		X	
Collect eDiary																X ^O	
Schedule next visit / contact	X	X	X		X		X		X	X		X		X		X	

[Abbreviations and footnotes are presented on the following page.]

Abbreviations used in the Schedule of Events for “CSL830-Interrupted” Subjects and “CSL830-Naïve” Subjects:

DVT = deep vein thrombosis; eCRF = electronic case report form; eDiary = electronic diary; CCI
; HAE = hereditary angioedema; CCI ; med = medication; PE = pulmonary embolism; CCI

Notes to the Schedule of Events for “CSL830-Interrupted” Subjects and “CSL830-Naïve” Subjects:

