All CSL830 dose increases are optional, and will be made only in subjects who are eligible, at the sole discretion of investigator. CSL830 dose increases may be made in increments of 20 IU/kg up to a maximum dose of 80 IU/kg. Subjects who are randomized to treatment with 40 IU/kg CSL830 and who are eligible for a dose increase may undergo up to 2 independent 20 IU/kg dose increases (at the sole discretion of the investigator), up to a maximum dose of 80 IU/kg. Subjects who are randomized to treatment with 60 IU/kg CSL830 and who are eligible for a dose increase may undergo a single 20 IU/kg dose increase (at the sole discretion of the investigator), up to a maximum dose of 80 IU/kg.

Assessment of Subject Weight

The weight of the subject is assessed at study visits. The baseline body weight for “CSL830-Naïve” and “CSL830-Interrupted” Subjects will be recorded at Screening. The baseline body weight for “CSL830-Continuation” Subjects will be recorded at the CSL830_3001 End of Study Visit.

The actual dose of CSL830 will be adjusted, if necessary. The actual dose administered will be based on the weight at Day 1 of Treatment Period 1 and will only be adjusted if the patient has a body weight change of more than 10% compared to baseline. If a new body weight is used, this weight will become the new baseline weight and subsequent weight measures will be compared to this. If there is a change of more than 10% compared to this new baseline weight the dose will be adjusted again. This will be repeated throughout the study.

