8.4.2 Screening

The eligibility of “CSL830-Naïve” Subjects and “CSL830-Interrupted” Subjects will be assessed at a Screening Visit conducted within the 4 weeks before Treatment Period 1.

The Screening Visit and the Day 1 Visit of Treatment Period 1 can occur on the same day. If a subject fails Screening at a combined Screening Visit / Day 1 Visit, then the subject will be treated as a screen failure.

“CSL830-Naïve” Subjects include the following:

- Subjects who did not participate in CSL830_3001.
- Subjects who participated in CSL830_3001 but did not receive blinded investigational product as a part of that study.

NOTE: For “CSL830-Naïve” Subjects, the first study visit is the Screening Visit.

“CSL830-Interrupted” Subjects include the following:

- Subjects who completed participation in study CSL830_3001, but who delayed entry into the current study (ie, > 1 week between the End of Study Visit of CSL830_3001 and the first visit of CSL830_3002 Treatment Period 1).

NOTE: For “CSL830-Interrupted” Subjects, the first study visit is the Screening Visit.

If a potential subject was not entered into Treatment Period 1 of the current study within the 4 weeks following the Screening Visit, the potential subject may attend a second Screening Visit (for a maximum of 2 Screening Visits per subject). In the event that a potential subject is screened twice, all Screening Period assessments including medical history must be repeated at the second Screening Visit and these finding / results will supersede those from the previous Screening Visit. CCI [REDACTED]

The following procedures will be conducted and documented at the Screening Visit:

- Written informed consent/assent (as appropriate).
- Review of inclusion and exclusion criteria.
- Develop an individual acute action plan, including assessment of subject’s ability to manage HAE attacks independently or with assistance.
- Demographics.
- Clinically significant history from the previous 6 months.
- Vital signs, including weight and height.
- Physical examination.
- Indwelling venous catheter is present (yes/no).
- Assess risk of DVT and PE.

- CCI [REDACTED]

CCI

- Start monitoring of AEs.
- Record prior / concomitant therapies, including therapy relating to HAE in the previous 3 months.
- Confirm access to on-demand medication for the treatment of breakthrough HAE attacks.

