^A To be updated (as needed) in order to provide a complete CSL830_3002 subject record.

^B The results of the urine pregnancy test conducted at the end of study visit can only be used to satisfy the applicable eligibility criterion if the CSL830_3001 End of Study Visit and the first visit of CSL830_3002 Treatment Period 1 (ie, Day 1) occur on the same day. Otherwise, a new pregnancy test must be performed at the first study visit in CLS830_3002 Treatment Period 1 in order to confirm eligibility.

Subjects who fulfill the inclusion/exclusion criteria (ie, eligible subjects) will be entered (randomized) into Treatment Period 1. If the subject is not eligible for the Treatment Period 1, the primary reason for screen failure must be entered in the eCRF.

The following assessments will be conducted by the investigator or delegate for all study subjects, unless otherwise noted:

- Review of inclusion / exclusion criteria in order to confirm eligibility to participate in the current study.
- Update demographics and medical history (as needed).
- Enroll subject into the study and randomize subject to a study treatment arm via interactive response technology.
- Dispense eDiary to subject.
- CCI [REDACTED]

- Obtain blood samples for the following [applicable to all “CSL830-Naïve” and “CSL830-Interrupted” Subjects AND “CSL830-Continuation” Subjects who did not complete the assessments at the CSL830_3001 End of Study Visit, only]:
 - Hematology.
 - Biochemistry.
 - Coagulation.
 - Viral serology.
 - Assessment of antibodies against C1-INH.
- Assess risk of DVT and PE [applicable to “CSL830-Continuation” Subjects who did not complete the assessments at the CSL830_3001 End of Study Visit, only].
- **CCI** [REDACTED]
- Obtain a urine sample for urinalysis [applicable to all “CSL830-Naïve” and “CSL830-Interrupted” Subjects AND “CSL830-Continuation” Subjects who did not complete the assessments at the CSL830_3001 End of Study Visit, only].
- For female subjects, obtain a urine sample for dipstick pregnancy testing to assess eligibility prior to randomization and dosing [applicable to all “CSL830-Naïve” Subjects and “CSL830-Interrupted” Subjects; also applicable to all “CSL830-Continuation” subjects if their CSL830_3001 End of Study Visit and their first visit of CSL830_3002 Treatment Period 1 (ie, Week 1, Day 1) occur on different days].
- Subject height [applicable to “CSL830-Continuation” Subjects, only].

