3.2 Study Treatment

The doses of CSL830 (40 IU/kg and 60 IU/kg) to be assessed in the current study were selected based on the results of the CSL830_2001 study.

A subject will be randomized to one of 2 treatment groups (CSL830 40 IU/kg or CSL830 60 IU/kg) and will administer CSL830 via a single SC injection, twice weekly. 40 IU/kg CSL830 is equivalent to a volume of 0.08 mL/kg; 60 IU/kg CSL830 is equivalent to a volume of 0.12 mL/kg. The volume to be administered (planned volume) is based on treatment assignment, a subject's baseline body weight (Day 1, Treatment Period 1), and rounding (i.e., up to the nearest whole mL). For those subjects who experienced a body weight change of more than 10% relative to baseline, the dose is to be adjusted and subsequent weight measurements are to be compared to the new weight. For those subjects who experience a body weight change of more than 10% relative to the new weight, the dose is to be adjusted again. This is repeated throughout the study. To promote compliance, the twice weekly administration of CSL830 should be scheduled on fixed days of the week (e.g., Monday and Thursday). The suggested interval between each administration of CSL830 is 3 or 4 days. In addition, CSL830 should be administered at approximately the same time on each day. A missed injection should be administered as soon as possible, unless within 24 hours of the next scheduled injection; in this situation, the missed injection should be omitted, and the administration of CSL830 should occur at the next scheduled day and time.

Beyond the Week 53 Visit, the volume to be administered (planned volume) is based on treatment assignment, a subject's body weight, and rounding (i.e., the actual dose of CSL830 that is assigned will be rounded (i.e., up or down) to the nearest 1000 IU for subjects

weighing ≥ 40 kg; subjects weighing < 40 kg will continue to undergo rounding as during Treatment Periods 1 and 2 (i.e., rounded up to the nearest 500 IU, for further details please see Country-Specific Protocol Amendment No. 1 (United States), dated 10 July 2015).

If a subject requires the use of C1-INH medication for the treatment of HAE attacks within 24 hours before a scheduled injection of CSL830, the scheduled injection may be delayed by up to 24 hours.

CSL830 Dose Increase

Some subjects may be eligible to increase the dose of CSL830 to which they were randomized at the beginning of Treatment Period 1.

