4.7.3 Vital Signs and Body Weight

Results of vital signs and body weight will be summarized by visit. Descriptive statistics for baseline and each treatment visit will be displayed. Descriptive subgroup analysis will be done for subjects who use any oral Prophylaxis for Treatment of HAE during the study.

Baseline will be Week 1 Day 1 for all “CSL830-Naïve” and “CSL830-Interrupted” Subjects and “CSL830-Continuation” Subjects who did not complete the assessments at the CSL830_3001 End of Study Visit. For “CSL830-Continuation” Subjects who complete the assessments at the CSL830_3001 End of Study Visit, these assessments will be the baseline. All vital signs and body weight data will be listed and abnormal results will be flagged.

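### SAP 4.7.3 takes the vital-sign and weight baseline of Naïve and Interrupted subjects from Day 1, but the protocol schedules their only pre-dose measurement at Screening

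*SAP*

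**What the plan says.** SAP 4.7.3 gives one rule for vital signs and body weight: "Baseline will be Week 1 Day 1 for all" CSL830-Naïve and CSL830-Interrupted subjects. Continuation subjects without the assessments from the CSL830_3001 End of Study Visit are treated the same way; those who have them use those values. The tables are descriptive: "Descriptive statistics for baseline and each treatment visit will be displayed". There is no provision for a Screening value or for the last value before dosing.

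The protocol places the measurement elsewhere. The Screening procedures in 8.4.2 include "Vital signs, including weight and height". The Day 1 list in 8.4.3.1 names neither vital signs nor weight; its only body measurement is "Subject height [applicable to “CSL830-Continuation” Subjects, only".

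On weight, protocol 3.2 says that the baseline for Naïve and Interrupted "Subjects will be recorded at Screening". The next paragraph of 3.2 ties the administered dose to a Day 1 weight. SAP 3.2 bases the planned volume on "baseline body weight (Day 1, Treatment Period 1), and rounding".

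**The concern.** The SAP names a visit at which the protocol does not schedule the measurement. Vital signs and body weight are listed in SAP 2.2.1 among the secondary safety endpoints, and safety is the primary objective of the study. SAP 4.12 plans no imputation.

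Applied literally, the rule drops some Naïve and Interrupted subjects from the baseline column, and they reappear from Week 9 onwards. A shift between the two columns could then reflect who is counted as well as any effect of treatment. The omission is also selective. Continuation subjects come from a crossover study in which each received CSL830 in one period, whereas Naïve subjects received no blinded product in that study. The baseline column would therefore lean towards subjects already exposed.

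If a programmer substitutes the Screening value, the table becomes sensible, but the step departs from the SAP. SAP 4.13 would then require it to be described and justified in the study report.

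**Working it through.** The plan states no figure that could be reproduced, so the check compares the texts.

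**1. Schedule of Events for Interrupted and Naïve subjects (protocol synopsis), read column by column.**

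| Row | Visits marked |
|---|---|
| Study center visit | Screening, Days 1, 4, 57, 113, 169, 197, 253, 309, 367 |
| Vital signs and weight | Screening, Days 57, 113, 169, 197, 253, 309, 367 |
| Clinical laboratory | Screening, Days 1, 57, 169, 197, 253, 367 |

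Vital signs are marked at 8 of the 10 listed center visits. The 10 − 8 = 2 without them are Day 1 and Day 4. Every vital-sign mark falls on a center visit. Moving the row one column to the right would put the Day 57 mark on Day 85, which is a telephone contact, so a shifted row does not explain the blank at Day 1.

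**2. Visit text.** Vital signs and weight appear in the Screening list (8.4.2) and not in the Day 1 list (8.4.3.1). They return at Week 9 (8.4.3.4). Some Day 1 items are redacted, but the vital-sign row of the schedule is legible and is blank on that day.

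**3. Count of scheduled values for these subjects.** Before the first injection: 1, at Screening, up to 28 days before Day 1. On Day 1: 0, unless the two visits are combined, which 8.4.2 allows. The Screening value is then also the Day 1 value.

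**4. Who lacks a baseline.** Let N be the number of Naïve and Interrupted subjects, and s the share of them with a combined visit. Relying on scheduled values only:

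subjects without a baseline = (1 − s) × N

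This is 0 if every visit was combined (s = 1) and all N if none was (s = 0). The documents give neither N nor s. The planned total of about 110 randomized subjects is not split by entry category, so no narrower range can be derived.

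**5. Comparison with the laboratory rule.** SAP 4.7.2.3 also sets baseline at Week 1 Day 1 for these subjects. It works there because blood is drawn on Day 1. The vital-sign rule uses the same visit without the same schedule behind it. The list of changes from the protocol in SAP 4.14 does not mention a move of this baseline, so nothing marks it as deliberate.

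**6. Continuation subjects.** The SAP rule fits the schedule. The CSL830_3001 End of Study value is used, and the assessment falls on Day 1 if it was not done then.

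**The case against.** The strongest reply is that very little depends on this. SAP 4.7.3 plans by-visit descriptive statistics and, unlike the laboratory section, no change from baseline. SAP 4.1 reports counts of missing and non-missing values, so a gap would be visible. All vital-sign and weight data are listed, so the Screening values are not lost. Randomization is stratified by entry category, so any loss should be similar in the two dose groups. Sites may in practice weigh subjects on Day 1, because protocol 3.2 refers to such a weight, and the electronic case report form on which the SAP is based is not available to check. All of this stands, and it keeps the point minor. It does not make the rule work: the schedule requires no Day 1 value, and the dosing sentence concerns weight, not blood pressure, pulse, temperature or respiratory rate.

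Three stronger readings are tempting, but the documents do not support them.

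- A reader might infer that the baseline column would contain almost only Continuation subjects. That needs combined visits to be rare, and the documents do not give their share.
- A reader might infer that treatment compliance is undermined. SAP 4.4.2 divides the reported volume by the planned volume, which is defined in SAP 3.2 and not through the baseline in 4.7.3. The 80% and 120% limits in SAP 4.11 select a listing for review before database lock; they do not exclude anyone automatically.
- A reader might infer that the SAP introduced the conflict over baseline weight. That conflict is already inside protocol 3.2, and SAP 3.2 follows one of its two statements.

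**Conclusion.** The rule in SAP 4.7.3 is wrong as written, and the consequence is small. Naïve and Interrupted subjects with separate Screening and Day 1 visits have no scheduled value at the visit that the SAP calls baseline. Their number is not given in the documents. The baseline and on-treatment columns of the descriptive vital-sign and weight tables would then cover different subjects. The primary person-time incidence rates and the secondary efficacy endpoints do not use this baseline.

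The conclusion assumes that the schedule was followed and that no unscheduled Day 1 measurement fills the gap. The inconsistency over baseline weight in protocol 3.2, carried into SAP 3.2, is a separate matter for the sponsor to reconcile.

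**What to change.** In SAP 4.7.3, define baseline as the last value before the first CSL830 injection in CSL830_3002. For Naïve and Interrupted subjects this is the Screening value when none was taken on Day 1. For Continuation subjects keep the present rule, the CSL830_3001 End of Study value where it exists. The wording also handles a repeated Screening Visit, whose results already replace the earlier ones under SAP 3.3.2.

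The cost is one SAP sentence, with no new data and no change to visits.

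Separately, the sponsor should reconcile the Screening and Day 1 statements on body weight in protocol 3.2 and the Day 1 statement in SAP 3.2. That needs a textual clarification in both documents, beyond the one sentence above. This review does not propose which weight should govern dosing.

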4.7.4 Physical examinations

Abnormal physical examination results will be recorded as either medical history (if prior to first study drug administration) or AEs (if after first study drug administration). Normal results will not be recorded. As such, physical examination results will be summarized through medical history and AEs only and there will be no summary of individual examination results.

All physical examinations dates will be listed.

4.7.5 Risk Assessment for Deep Vein Thrombosis and Pulmonary Embolism

The clinical model scoring system will be used for the risk assessment of deep vein thrombosis:

Clinical Feature	Score
Active cancer (treatment ongoing or within previous 6 months or palliative)	+1
Paralysis, paresis, or recent plaster immobilization of the lower extremities	+1
Recently bedridden for more than 3 days or major surgery, within 4 weeks	+1
Localized tenderness along the distribution of the deep venous system	+1
Entire leg swollen	+1
Calf swelling by more than 3 cm when compared with the asymptomatic leg (measured 10 cm below tibial tuberosity)	+1
Pitting edema (greater in the symptomatic leg)	+1
Collateral superficial veins (non-varicose)	+1
Alternative diagnosis as likely or greater than that of deep vein thrombosis	-2

Note: In subjects with symptoms in both legs, the more symptomatic leg is used.

Individual clinical feature scores and calculated risk scores will be recorded in the eCRF.

If a subject has a risk score of ≥ 1 , a lower extremity ultrasound examination will be arranged by the investigator to exclude deep vein thrombosis. If a deep vein thrombosis is confirmed on ultrasound examination, the event will be classified as an AESI and will be reported as a SAE.

The following clinical model scoring system will be used for the risk assessment of pulmonary embolism:

Clinical Feature	Score
Previous pulmonary embolism or deep vein thrombosis	+1.5
Heart rate >100 beats per minute	+1.5
Immobilization or surgery in the previous four weeks	+1.5
Clinical signs and symptoms of deep vein thrombosis (minimum of leg swelling and pain with palpation of the deep veins)	+3
Alternative diagnosis less likely than pulmonary embolism	+3
Hemoptysis	+1
Malignancy (on treatment, treated within the last 6 months, or palliative)	+1

Individual clinical feature scores and calculated risk scores will be recorded in the eCRF.

If a subject has a risk score of ≥ 2 , a computerized tomographic (CT) angiogram or appropriate investigation will be arranged by the investigator to exclude pulmonary embolism. If pulmonary embolism is confirmed on investigation, the event will be classified as an AESI and will be reported as a SAE.

The number and percentage of subjects with a risk score for deep vein thrombosis and pulmonary embolism of ≥ 1 or ≥ 2 (respectively) will be summarized at each visit.

CCI [REDACTED]

CCI [REDACTED]

[REDACTED]

[REDACTED]

[REDACTED]

[REDACTED]

[REDACTED]

[REDACTED]

[REDACTED]

CCI [REDACTED]

CCI [REDACTED]

[REDACTED]

[REDACTED]

[REDACTED]

[REDACTED]

[REDACTED]

CCI [Redacted]

CCI [Redacted]

- [Redacted]
- [Redacted]
- [Redacted]

[Redacted]

- [Redacted]
- [Redacted]
- [Redacted]
- [Redacted]
- [Redacted]
- [Redacted]

[Redacted]

[Redacted]

[Redacted]

CCI [Redacted]

[Redacted]

[Redacted]

[Redacted]

[Redacted]

CCI [Redacted]

[Redacted]

[Redacted]

[Redacted]

[Redacted]

CCI [Redacted]

[Redacted]

[Redacted]

CCI [Redacted]

[Redacted]

[Redacted]

[Redacted]

CCI [Redacted]

[Redacted]

[Redacted]

[Redacted]

[Redacted]

CCI [Redacted]

[Redacted]

CCI [redacted]

[redacted]

[redacted]

[redacted]

[redacted]

[redacted]

[redacted]

CCI [redacted]

[redacted]

[redacted]

[redacted]

[redacted]

[redacted]

CCI [Redacted]

[Redacted]

[Redacted]

CCI [Redacted]

[Redacted]

[Redacted]

[Redacted]

[Redacted]

[Redacted]

CCI
[Redacted text block]

- | [Redacted]
- | [Redacted]
- | [Redacted]
- | [Redacted]
- | [Redacted]
- | [Redacted]
- | [Redacted]

[Redacted text block]

CCI [Redacted]

[Redacted text block]

CCI [Redacted]

[Redacted]

[Redacted]

[Redacted]

[Redacted]

[Redacted]

[Redacted]

[Redacted]

[Redacted]

[Redacted]

[Redacted]

[Redacted]

[Redacted]

[Redacted]

CCI [Redacted]

CCI [Redacted]

[Redacted]

[Redacted]

[Redacted]

[Redacted]

- [Redacted]
- [Redacted]
- [Redacted]
- [Redacted]
- [Redacted]

CCI [Redacted]

[Redacted]

[Redacted]

- [Redacted]
- [Redacted]
- [Redacted]
- [Redacted]
- [Redacted]

CCI [Redacted]

CCI [Redacted]

- [Redacted]
- [Redacted]
- [Redacted]
- [Redacted]
- [Redacted]
- [Redacted]

[Redacted]

[Redacted]

[Redacted]

CCI [Redacted]

CCI [Redacted]

CCI [Redacted]

[Redacted]

CCI [Redacted]

CCI [Redacted]

CCI [redacted]
[redacted]
[redacted]
[redacted]

[redacted]
[redacted]

[redacted]
[redacted]
[redacted]

[redacted]
[redacted]
[redacted]

CCI [redacted]

CCI [redacted]
[redacted]
[redacted]
[redacted]

- | [redacted]
- | [redacted]
- | [redacted]

[redacted]
[redacted]

CCI [redacted]

CCI [redacted]
[redacted]
[redacted]
[redacted]
[redacted]
[redacted]
[redacted]
[redacted]

CCI [Redacted]

[Redacted]

[Redacted]

CCI [Redacted]

CCI [Redacted]

[Redacted]

[Redacted]

CCI [Redacted]

CCI [Redacted]

CCI [Redacted]

CCI [Redacted]

CCI [Redacted]

[Redacted]

[Redacted]

[Redacted]

[Redacted]

[Redacted]

[Redacted]

CCI [Redacted]

[Redacted]

[Redacted]

[Redacted]

[Redacted]

[Redacted]

CCI [Redacted]

CCI [Redacted]

CCI [Redacted]

CCI [Redacted]

[Redacted]

[Redacted]

[Redacted]

